7.2 Dose and treatment regimens

The study consists of a Screening Visit (Visit 1), a Lead-in Period Visit (Visit 2), a single-blind run-in period of 1 week and a randomization visit (Visit 3), followed by a 28-week randomized, double-blind treatment period and a 24-week extension period. Double-blind study medication will be dispensed every 4 weeks during the treatment period and every 8 weeks during Extension Period 1. Double-blind study medication will be dispensed every 3 months (13 weeks) during Extension Period 2. Instructions for dose preparation of the exenatide once weekly injection will be provided in the Instructions for Use.

AstraZeneca or a designated representative will provide all IPs. At each visit, patients will receive sufficient quantity of drug to last the duration of time between visits. In the event the patient loses her/his study medication, the study center should call into the IVRS/IWRS

system in order to allow the system to determine the appropriate alternative kit identification number(s) to be dispensed from the study center's remaining inventory.

Lead-in period (Visit 2, Week -1)

Patients will receive dapagliflozin placebo tablets to be taken daily for the 1-week placebo lead-in period, as well as an exenatide placebo injection to be taken once at the start of the placebo lead-in period. A medically qualified staff member will demonstrate preparing the study medication by reconstitution of the powder in the diluent provided for the patient or a designated caregiver, after which the patient (or designated caregiver) will administer the placebo injection. Patients will be instructed to continue taking metformin as directed during this period.

28-week Treatment period (Visits 3-12)

At Visit 3 patients will be randomly assigned to 1 of the 3 treatment arms and randomized study medication (injection and tablets) will be dispensed. For EQW and matching placebo, the doses of study medication will be taken at the study site. The injection must be administered immediately after preparation of the dose. Patients will subsequently self-administer EQW or matching placebo (or have it administered by a caregiver) once weekly relative to the date of the first dose of EQW (Visit 3 [Day 0]) through Visit 12 (Week 28/Study Termination). Patients will receive dapagliflozin or matching placebo tablets to be taken once daily through Visit 12 (Week 28/Study Termination).

On weeks of scheduled study visits, patients should bring their study medication with them to the study site (patients should be given instructions and supplies as appropriate for study medication transportation to ensure proper temperature control, etc.) and will self-administer EQW as directed by study-site personnel.

If a dose of EQW is missed, it should be administered as soon as noticed, provided the next regularly scheduled dose is due at least 3 days later. Thereafter, patients can resume their usual dosing schedule of once every 7 days (weekly).

If a dose of EQW is missed and the next regularly scheduled dose is due 1 or 2 days later, the patient should not administer the missed dose and instead resume EQW with the next regularly scheduled dose.

Doses of EQW or matching placebo are to be administered by SC injection in the abdomen, thigh, or upper arm. The site of injection should be rotated within or across regions on a regular basis so that the same site is not used repeatedly.

If a dose of dapagliflozin is missed, advise patients to take it as soon as it is remembered unless it is almost time for the next dose, in which case patients should skip the missed dose and take the medicine at the next regularly scheduled time. Advise patients not to take 2 doses of dapagliflozin at the same time.

Extension Period 1 (Visits 12 to 15)

Study medication will be dispensed every 8 weeks during this period.

Extension Period 2 (Visits 16 to 19)

Study medication will be dispensed every 3 months (13 weeks) during this period.

7.3 Labelling

Labels will be prepared in accordance with Good Manufacturing Practice (GMP) and local regulatory guidelines. The labels will fulfil GMP Annex 13 requirements for labelling. Label text will be translated into local language.

7.4 Storage

All study medications should be kept in a secure place under appropriate storage conditions. The IP label on the study medication kit specifies the appropriate storage.

7.5 Compliance

Patients will be asked to return all unused study medication and ancillary medication as well as empty packages and bottles to the clinic at each visit. The patient will be asked about compliance at each study visit; compliance will also be assessed based on returned amounts of investigational and ancillary products and reported dosing information. Patients judged to be non-compliant (defined as taking less than 80% or more than 120% of the prescribed dose of IP) may continue in the study, but should be counseled on the importance of taking their study medication and applicable ancillary medications as prescribed.

The administration of all study medications (including IPs) should be recorded in the appropriate sections of the eCRF. Treatment compliance (number of doses received relative to doses planned) will be summarized by treatment for the ITT Population.

7.6 Accountability

The study medication provided for this study will be used only as directed in the study protocol.

The study site personnel will account for all study medications dispensed to and returned from the patient.

Study site personnel will account for all study medications received at the site, unused study medications and for appropriate destruction. Certificates of delivery, destruction and return should be signed.

A drug disposition form will be provided to record all study medication dispensed to or returned from each patient. Upon completion of the study, all unused study medication, and copies of completed drug disposition forms should be returned to the Sponsor (or designee).

Used study medication kits may be disposed at study sites after accountability has been verified by the Sponsor (or designee) and will not be returned to the Sponsor (or designee).

For unused study medication, a clinical supplies return authorization form (CSRAF) will be completed by the clinical research associate at the closeout visit. The completed CSRAF should be enclosed with each return drug shipment to the Sponsor (or designee). The study site personnel must maintain documentation of any missing, damaged, or unreturned study medication.

7.7 Concomitant and other treatments

Patients must follow the medication restrictions outlined in the inclusion and exclusion criteria (Section 3.1 and Section 3.2, respectively) during the study. Dosages for certain concomitant medications should be maintained constant during the study, unless instructed otherwise by the investigator or a treating physician. Any change in regimen for any concomitant medication, including restricted concomitant medications, must be reported to the Sponsor.

Metformin and rescue therapy will not be provided in pre-packaged kits by the Sponsor and will be sourced locally by the site in cooperation with the CRO and in accordance with the approved package labeling.

The table below lists prohibited medications and the applicable time frames.

Restricted Medication/Class of drug:	Usage
Antihypertensive agents	Patient must either not be treated with or has been on a stable treatment regimen for a minimum of 2 months prior to Visit 1 (Screening).
Thyroid replacement therapy	Patient must either not be treated with or has been on a stable treatment regimen for a minimum of 2 months prior to Visit 1 (Screening).
Antidepressant agents	Patient must either not be treated with or has been on a stable treatment regimen for a minimum of 2 months prior to Visit 1 (Screening).
Antihyperglycemic therapy	Administration of any antihyperglycemic therapy, other than metformin, for more than 14 days (consecutive or not) during the 12 weeks prior to enrollment is prohibited.
Antihyperglycemic therapy	Administration of any antihyperglycemic therapy, other than metformin, at any dose, at any time during the 4 weeks prior to the enrollment visit is prohibited.
Exenatide (including BYETTA [®] , BYDUREON [™] , or exenatide suspension) or any GLP-1 analog	Any prior exposure is prohibited (or use of non-study products during the study).
Dapagliflozin (FORXIGA, FARXIGA) or any	Any prior exposure is prohibited (or use of non-study

Restricted Medication/Class of drug:	Usage
SGLT-2 inhibitor	products during the study).
Any DPP-4 inhibitor	Prohibited within 3 months prior to Visit 1 (Screening) and during the study.
Systemic corticosteroids by oral, intravenous, intra-articular, or intramuscular route	Prohibited within 3 months prior to Visit 1 (Screening) and during the study.
Potent, inhaled, or intrapulmonary (including ADVAIR®) steroids known to have a high rate of systemic absorption ^a : 
 • beclomethasone dipropionate nasal and oral inhalation (Beclovent, Beclonase, Qnasl, Qvar) • budesonide nasal and oral inhalation (Pulmicort, Symbicort, Rhinocort) • flunisolide oral inhalation aerosol and nasal route (Aerobid, Aerospan, Nasalide, Nasarel) • fluticasone propionate aerosol and powder (Advair, Flovent) • mometasone furoate aerosol and powder inhalation (Asmanex, Dulera) 	Prohibited within 3 months prior to Visit 1 (Screening) and during the study.
Prescription or over-the-counter weight loss medications	Prohibited within 3 months prior to Visit 1 (Screening) and during the study.

^a Not excluded: ciclesonide oral inhalation and nasal spray (Alvesco, Omnaris, Zetonna). This is not a comprehensive listing. If the exclusion status of any concomitant medication is in question, please contact the Medical Monitor for discussion.

The following steroids are permitted during the study: ciclesonide oral inhalation and nasal spray (Alvesco, Omnaris, Zetonna).

7.7.1 Metformin

Up to Visit 20 (Week 114), patients should continue to administer the same type and dose of metformin therapy they were using at study entry. Metformin will be prescribed by the investigator and should be administered and stored according to product and country-specific labeling.

7.7.2 Rescue therapy

Patients who require rescue therapy (ie, FPG rescue criteria met) will receive open-label titrated basal insulin, as prescribed by the investigator (see Section 4.2). Patients should continue receiving study medication while receiving rescue therapy. Patients must first complete the Rescue visit procedures before receiving open-label rescue therapy.

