3.6 Methods for ensuring blinding

During the Lead-in Period, patients will be treated with single-blinded placebo (tablets and injection). Patients, the investigator, study site personnel, and Sponsor personnel involved with data review and analysis will be blinded starting at Visit 3 (randomization), and will remain blinded to study treatment throughout the 28-week randomized treatment period. Only patients and investigators will remain blinded during the 24-week extension period. To preserve the blinding, access to the treatment codes will be limited to personnel not involved in the daily conduct of the trial or data review and analysis.

No member of the study team in AstraZeneca, at study sites, or any contract research organization (CRO) handling data will have access to the randomization scheme during the conduct of the study with the exception of AstraZeneca's Investigational Product Services and Patient Safety.

The randomization schedule for blinding of randomized treatment will be maintained by AstraZeneca or representative and will not be disclosed until after the first database lock at the end of the initial 28-week treatment period. AstraZeneca and its applicable representative(s) will be unblinded in Extension Periods 1 and 2 (ie, from Week 28 onwards). Sites and patients will remain blinded during Extension Periods 1 and 2.

The results for FPG, HbA1c, urine glucose/creatinine ratio, urine glucose, and urine creatinine are blinded to the investigator for all visits except Visits 1 to 3. FPG and HbA1c values are

blinded to the investigator site until the unblinding criteria for rescue therapy are met. Once the criteria are met, fasting plasma glucose and HbA1c will be reported to the site for an individual patient (ie, if FPG >270 mg/dL from Week 8 to Week 12 [excluding Week 12], or FPG >240 mg/dL from Week 12 to Week 20 [excluding Week 20], or FPG >200 mg/dL from Week 20 to Week 28 [including Week 28]). Previous values will remain blinded and the site will only receive the values going forward from the point the criteria were met.

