4.2 Treatment period

After the randomization visit (Visit 3), patients will complete study visits at 1- to 4-week intervals until the end of the randomized treatment period (Visit 12, Week 28). Starting at Week 8, patients with inadequate glycemic control based on progressively stricter glycemic criteria as outlined in [Table 3](#) will remain in the study and will receive open-label rescue therapy with basal insulin.

Table 3 **Criteria for initiation of rescue therapy during the randomized treatment period**

Period	Central laboratory FPG
From Visit 7/Week 8, inclusive, up to and including the day before Visit 8/Week 12	FPG >270 mg/dL (15 mmol/L)
From Visit 8/Week 12, inclusive, up to and including the day before Visit 10/Week 20	FPG >240 mg/dL (13.2 mmol/L)
From Visit 10/Week 20, inclusive, up to and including Visit 12/Week 28 and all unscheduled visits through the day prior to Visit 13/Week 36	FPG >200 mg/dL (11.1 mmol/L)

Note: Repeat FPG testing required for confirmation before rescue initiated.

Abbreviation: FPG fasting plasma glucose

Patients with a central laboratory FPG value meeting the lack of glycemic control criterion at a pre-specified visit will be scheduled for a follow-up visit (within 3 to 5 days) to obtain a second central laboratory FPG value and review the patient's glucose meter readings. If the repeat central laboratory FPG value still meets the criterion, the patient may receive rescue therapy. Patients should continue receiving study medication while receiving rescue therapy. Patients who meet rescue criteria in the double-blind treatment period must first complete the Rescue visit procedures before receiving open-label rescue therapy, to ensure that important trial endpoint measurements are collected.

Patients who receive rescue therapy should be instructed to perform the 6-point SMBG profile before returning to the clinic for the Rescue Visit; see Section 5.1.5 for additional details.

Rescued patients with central laboratory HbA1c values >8.0% despite a maximum tolerated dose of rescue therapy for 12 weeks will be discontinued from the study and referred for additional antihyperglycemic therapy.

4.2.1 Treatment Period Visits (Visits 4 to 11, Weeks 1, 2, 4, 8, 12, 16, 20, and 24)

Prior to these visits, patients are to have fasted overnight (at least 8 hours). Patients should delay administering their morning dose of metformin and study medication on the morning of the study-site visit.

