4.3 Extension Period 1 (24-week Extension period)

Patients will return for follow-up visits every 8 weeks during the long-term site-and patient-blinded Extension Period 1. Patients will monitor their fasting blood glucose levels at least once a week and will continue to enter the results into the patient diary. Diet and lifestyle modification will be reinforced at each visit during this period. Patients will be contacted approximately monthly between visits (as described in [Table 2](#)).

The need for initiation of rescue therapy will be assessed based on criteria in [Table 4](#). Patients must first complete the Rescue visit procedures before receiving open-label rescue therapy.

Table 4 **Criteria for initiation of rescue therapy during Extension Period 1**

Period	Central Laboratory HbA1c
From the day of Visit 13/Week 36 up to and including Visit 15/Week 52 and all unscheduled visits through the day prior to Visit 16/Week 65	HbA1c >8.0%

Note: Rescue upon receipt of HbA1c results. No repeat testing required for confirmation.

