4.3.1 Extension Period 1 Visits (Visits 13 and 14, Weeks 36 and 44)

Prior to these visits, patients are to have fasted overnight (at least 8 hours). Patients should delay administering their morning dose of metformin and study medication on the morning of the study-site visit.

The following will be performed during these visits:

- IVRS will be contacted to register the visit.
- AEs, potential CV event triggers (Section 6.8.1), and concomitant medications will be reviewed.
- A brief physical exam will be conducted (refer to Section 5.2.2).
- Vital signs (sitting systolic and diastolic BP and HR) will be assessed.
- Body weight will be measured.
- Blood samples will be collected **prior to administration of study medication** for the following assessments:
 - Chemistry and hematology
 - HbA1c (need for rescue will be evaluated)
 - Fasting plasma glucose
 - Serum creatinine (calculated creatinine clearance; Cockcroft-Gault formula).
- Urine will be collected for the following assessments:
 - Urinalysis
 - Urine glucose/creatinine ratio

- Pregnancy test for all female patients, unless patient has had a hysterectomy.
- Patient diary will be reviewed.
- Visit 14 only: Patients will be instructed to complete 6-point SMBG profiles on any 3 days in the week prior to Visit 15.
- Hypo glycemia episodes will be assessed.
- Diet and exercise counseling will be provided.
- Glucose meter and supplies will be provided.
- Study medication compliance will be reviewed.
- Study medication will be dispensed every 8 weeks during Extension Period 1: Visits 13 and 14. Study site personnel will monitor administration of injectable study medication (if the patient is due for an injection at the time of the visit).
- Instructions, reminders, and supplies (as appropriate) will be given to the patient (or designated caregiver) for proper transportation and storage of the study medication (to ensure temperature control, etc.).
- Rescue medication will be dispensed at Visits 13 and 14 if criteria for rescue medication are met (refer to [Table 2](#)).
- Used/unused study medication will be collected.
- Between-visit telephone contacts will take place between Visits 13 to 16 for collection of safety information.

4.4 52-week Extension Period (Extension Period 2)

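### Rescue switches from FPG to HbA1c at Week 36, but the result-release rule and three other sections still run on FPG

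*Protocol*

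**What the plan says.** **Rescue criteria.** Table 3 (Section 4.2) uses FPG. Its last row, FPG >200 mg/dL, runs from Week 20 "up to and including Visit 12/Week 28 and all unscheduled visits through the day prior to Visit 13/Week 36", and a repeat FPG is required before rescue. From Week 36, Table 4 (Section 4.3) uses HbA1c >8.0%. Table 5 (Section 4.4) uses HbA1c >7.5% from Week 65 and >7.0% from Week 91 to the day before Week 104. The note to Table 4 reads "Rescue upon receipt of HbA1c results. No repeat testing required for confirmation", and Table 5 carries the same note. The visit lists in Sections 4.3.1 and 4.4.1 agree: "HbA1c (need for rescue will be evaluated)".

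**Release of results.** Section 3.6 masks FPG and HbA1c from Visit 4 onward. They stay "blinded to the investigator site until the unblinding criteria for rescue therapy are met". The criteria then listed are three FPG thresholds, the last being "or FPG >200 mg/dL from Week 20 to Week 28 [including Week 28]". Earlier values stay masked, and "the site will only receive the values going forward from the point the criteria were met".

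**Other sections.**
- Section 7.7.2: "Patients who require rescue therapy (ie, FPG rescue criteria met) will receive open-label titrated basal insulin". It refers only to Section 4.2.
- Section 4.5 (Visits 15 and 19, and early termination or rescue in the extensions) puts the rescue evaluation against FPG and lists HbA1c without it.
- Section 5.1.5 has the pre-rescue 6-point SMBG done once a repeat FPG has confirmed the need for rescue.
- Section 4.3.1 says "Rescue medication will be dispensed at Visits 13 and 14 if criteria for rescue medication are met" but sends the reader to Table 2, the visit schedule, not Table 4.

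**The concern.** The site is told to rescue on an HbA1c result that the blinding section does not let it see. The FPG wording fits the first 28 weeks and appears not to have been revised for the extensions, where the trigger is a different analyte with a different confirmation rule.

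A patient above the HbA1c threshold could be rescued late or not at all, and sites could differ according to which section they follow. About 100 sites are planned, and the HbA1c-based period runs from Week 36 to Week 104 (104 − 36 = 68 weeks). The endpoints exposed are the exploratory Week 52 and Week 104 ones: directly, the proportion rescued or discontinued for lack of glycemic control; indirectly, the efficacy measures that depend on who received insulin and when. Section 3.9 also discontinues rescued patients whose central-laboratory HbA1c stays above 8.0% after 12 weeks of maximum tolerated rescue. For a patient first rescued in an extension, that rule too needs an HbA1c value for which Section 3.6 has no release criterion.

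**Working it through.** No calculation underlies this point, so the check sets the trigger at each scheduled visit beside the Section 3.6 release list.

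| Visits (weeks) | Rescue trigger | Release criterion in 3.6 |
|---|---|---|
| 7 (8) | FPG >270 mg/dL (Table 3) | FPG >270 mg/dL |
| 8, 9 (12, 16) | FPG >240 mg/dL (Table 3) | FPG >240 mg/dL |
| 10, 11, 12 (20, 24, 28) | FPG >200 mg/dL (Table 3) | FPG >200 mg/dL |
| 13, 14, 15 (36, 44, 52) | HbA1c >8.0% (Table 4) | none |
| 16, 17 (65, 78) | HbA1c >7.5% (Table 5) | none |
| 18 (91) | HbA1c >7.0% (Table 5) | none |

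**Count.** FPG-trigger visits: 1 + 2 + 3 = 6, of which 6 have a matching release rule. HbA1c-trigger visits: 3 + 2 + 1 = 6, of which 0 do.

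**Who is seen.** Release, once triggered, continues for that patient. So the site sees extension HbA1c only for patients who crossed an FPG threshold by Week 28. Those thresholds are the Table 3 rescue thresholds, so these are largely patients already identified for rescue. For patients whose first failure is an HbA1c above the limit in an extension, no release criterion applies.

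**The other sections against Tables 4 and 5.**
- 7.7.2 equates need for rescue with the FPG criteria. A patient who meets only the HbA1c criterion falls outside that definition.
- 4.5 repeats the Week 28 wording of 4.2.2, where FPG is correct. At Visit 15 (Week 52) Table 4 makes HbA1c the criterion. At Visit 19 (Week 104) no rescue evaluation is needed, because Table 5 ends the day before and study medication stops.
- 5.1.5 waits for a confirmatory FPG, whereas Tables 4 and 5 act on one HbA1c.

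**Two smaller slips.** Table 3 applies FPG >200 mg/dL to unscheduled visits up to the day before Week 36, while the 3.6 list stops at Week 28. The gap is 36 − 28 = 8 weeks and concerns unscheduled visits only. The Table 2 reference in 4.3.1 should be to Table 4.

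**The case against.** The best defence is that the intended rule is plain. Sections 4.3 and 4.4 say rescue is assessed against Tables 4 and 5, the visit lists attach the evaluation to HbA1c, and the table notes presuppose that the site receives the result. No section gives a competing FPG threshold from Week 36. Sections 5.1.5 and 7.7.2 refer to Section 4.2 and can be read as describing the treatment period. Section 5.1.5 only times the SMBG, lets the investigator omit it, and so cannot block rescue. Section 4.5 gives no FPG threshold and has no effect at Week 104. The six-visit count is one omission seen at six visits and measures no harm. Sites and patients stay blinded to treatment, so no bias between arms is shown. Weekly home fasting glucose, diary review and the general instruction in 3.9 to rescue on loss of glucose control also offer some protection.

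Most of this stands as a limit on the consequences. Release was probably intended, and Section 4.5 matters only at Week 52 and at extension rescue visits. But it does not remove the conflict. Section 3.6 is the operative blinding rule, and it introduces its list with *ie*, which makes the list closed. A laboratory or site that follows it withholds the value that Tables 4 and 5 require the site to act on. None of the safeguards supplies that HbA1c.

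**Conclusion.** The inconsistency is real and should be fixed. The HbA1c rescue rule itself is clear; the fault is that Section 3.6 provides no route for the triggering value to reach the site, and that 4.5, 5.1.5 and 7.7.2 still describe FPG-based rescue. In size, 0 of 6 scheduled HbA1c-trigger visits have a release criterion, against 6 of 6 for FPG. How many patients this would affect cannot be derived from the protocol, and any delay or variation between sites depends on sites or the laboratory applying 3.6 as written.

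The sample size and the Week 28 primary and secondary endpoints are unaffected, because the FPG criteria agree across sections for scheduled visits through Week 28. The exposure is confined to patient management from Week 36 and to the exploratory Week 52 and Week 104 endpoints.

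**What to change.** Keep Tables 3 to 5 as the governing criteria and conform the rest:

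- **3.6:** extend release on FPG >200 mg/dL to the day before Week 36. Then add release on HbA1c >8.0% (Week 36 to the day before Week 65), >7.5% (Week 65 to the day before Week 91) and >7.0% (Week 91 to the day before Week 104).
- **7.7.2:** define need for rescue as meeting the criteria of Table 3, 4 or 5, and cite Sections 4.2 to 4.4.
- **4.5:** move the rescue note from FPG to HbA1c for Week 52 and drop it for Week 104.
- **5.1.5:** limit the repeat-FPG wording to rescue under Table 3, and add an HbA1c result under Table 4 or 5 as a trigger for the pre-rescue SMBG.
- **4.3.1:** refer to Table 4.

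The cost is wording in five sections and a central-laboratory alert specification. No visits or samples are added.
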